### 17.3 Subgroup analysis

A subgroup analysis of gait quality, including left and right lower extremity single support time, initial double support time, step length, and stride width will be performed in centers using GAITRite equipment and software and compared between randomized groups. The sample available for this sub-analysis is expected to be approximately 30% of the total study population.

### 17.4 Sample Size

Computations for sample size and power are based on effect sizes derived from internal study data and the relevant clinical literature for the primary endpoint. For the Ekso intervention group, the postulated effect (derived from internal study data) is a mean change from baseline in gait speed of 0.11 m/s, with a corresponding standard deviation of 0.18 m/s. For the active control group, the postulated effect is a mean change from baseline in gait speed of 0.078 m/s (derived from the relevant clinical literature), with a corresponding standard deviation of 0.108 m/s.

The passive control group is postulated to have a mean change of zero with the same standard deviation as active control, or 0.108 m/s. Sample size and power are then computed for both statistical tests cited above: superiority of Ekso to passive control and non-inferiority of Ekso to active control.

Under 2:2:1 randomization with a desired power of 80%, the required sample size for superiority of Ekso intervention to passive control is 38 subjects with evaluable data in the Ekso group and 19 in passive control (incorporating the 2:1 Ekso: passive control randomization). For non-inferiority of Ekso to active control, the groups are of equal size and the required sample size is 37 per group.

Taking the greater of these numbers for each randomized group, total sample size under 2:2:1 randomization is therefore 38 for Ekso intervention, 38 for active control and 19 for passive control, a total of 95. To account for possible attrition as well as potential variance from the postulated effects, up to 127 subjects in the randomized group will be enrolled.

## 18. Visits and Visit Windows

The following are the planned Participant visits and their associated windows. Missed visits should be made up so that testing can be conducted within the appropriate window of time.

**Table 4 – Planned Participant Assessments and Assessment Windows**

Time point	Window
Baseline	No more than 30 days prior to start of training
6 Weeks(after 18 session)	No more than 1 week after session 18
12 Weeks (after 36 session)	No more than 1 week after session 36
6 Months	+/- 3 weeks

## **18.1 Handling of Dropouts, Treatment Rescues and Missing Data**

Values for missing data will not be imputed, but exploratory analyses may be performed using the last real assessment for that patient (LOCF).

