**Footnotes (Table 2):**

† Height may be obtained verbally; weight must be measured via scale. Calculate BMI using NIH National Heart Lung and Blood Institute calculator at: [http://www.nhlbi.nih.gov/health/educational/lose\\_wt/BMI/bmicalc.htm](http://www.nhlbi.nih.gov/health/educational/lose_wt/BMI/bmicalc.htm)

\* Skin assessment to be performed before and after training sessions

• Maximum Borg to be done during session 1 then during weekly sessions (every third session) thereafter, and after 6 minute walk test during evaluations

\*\* Assessments to be performed outside of exoskeleton or any body weight support and on a non-training day.

◦ Vital signs (BP and HR) will be measured as follows:

- °° Upon relaxation (5 minutes) in sitting position after arrival. After 1 minute of standing (may hold on to something for balance or use standing in frame as needed)
- °°° Vitals should be taken in sitting before and immediately after 6 minute walk
- ↳ To be taken prior to 10MWT
- " To be taken prior to each session and needed only if orthostatic hypotension was present at the time of the previous session and/or if symptomatic upon standing at the time of the current session.

♦ Run In will follow Group 1 assessments but will not complete the follow up evaluation visit and assessments

^ To be obtained during Screening, and if participant passes screening can be used for Baseline

† Numeric Pain Scale: to be completed before and during session 1 and weekly thereafter

¤ To be done by blinded evaluator for comparison to week 6, 12, 24 (midpoint, endpoint, and follow-up) evaluation visit results.

☆ Done by blinded evaluator for comparison. Testing to be done according to ISNCSCI instructions (supine, using the correct limb positioning and angles for resistance)

 May occur over one or two visits

 B = before session, D = during session, A = after session

 Passive Group 3 will complete all evaluations at Baseline, Week 6 and week 12, the same as Groups 1 and 2, then have the option (per participant decision) to undergo 12 weeks of training using the exoskeleton or standard gait training. The optional 12 week period will consist of training only. No further evaluations will be completed at this time.

Update Concomitant Medication Log accordingly

To include shoulder flexion/extension, abduction/, and triceps

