Skin assessment with focus on back, sacrum, shins, and feet to be collected before and after each training session

To be collected outside of the exoskeleton or any body weight support, and prior to any training session; can be used to assess readiness to transition to overground training weekly.

**Screening:** (10MWT) 1 walk with or without braces at self-selected speed to confirm qualification self-selected speed of <0.44 m/s. A second trial may should be done if first trial is close to 0.44 m/s.

**Baseline:** up to 8 trials (total) of 10MWT (2 trials each, with and without braces at both self-selected and fast speeds (to be done by blinded evaluator)

**Every 3rd session:** 10MWT (2 trials, without braces at self-selected speed), every 3rd session, if possible. The walk is done without braces (to determine neurological recovery changes). Pt can complete second walk to donn Ekso, or to donn the harness for BWSTT (depending on randomization and tolerance).

**Evaluations** at 6, 12, 24 weeks (midpoint, endpoint, and follow-up): up to 8 trials (total) of 10MWT (2 trials each, with **baseline** device/braces at both self-selected and fast speeds, then 2 trials with **current** device/braces at self-selected and fast speeds, performed with whatever assistive devices are needed for safe ambulation (to be done by blinded evaluator)

The first training in the exoskeleton occurs separately from screening and baseline data collection

Form to be completed at the time of study completion or at any time of early termination

Use baseline assistive device(s) and brace(s) for all TUG and 6 MWT assessments.

Every 3rd session

Score WISCI for current device/braces at self-selected speed

Table 3 - Therapist Assessments, and Data Collection Intervals (to be completed by the lead treating PT). Report of pain/injury to be completed by all participating session staff	Baseline Visit After 1 st Session	Session Evaluations GROUPS 1 & 2 (and Run-In) Sessions 1-36			Evaluations ALL GROUPS (including Run-In) After session 18** (Week 6) Midpoint (+/- 1 week of completing session 18)	Evaluations ALL GROUPS (including Run-In) After session 36** (Week 12) Endpoint (+/- 1 week of completing session 36)
Assessment		B	D	A		

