## **17. Statistical Methods**

### **17.1 General Principles**

The primary analysis for all baseline characteristics and study outcomes will include all available data for all enrolled subjects. Standard summary statistics will be calculated for all study variables. For continuous variables, statistics will include means, standard deviations, medians and ranges. Categorical variables will be summarized in frequency distributions.

Statistical analyses will be conducted according to the principles of intent-to-treat, under which subjects will be evaluated according to their randomized assignment regardless of the treatment actually received. P-values for tests of superiority will be two-sided and for non-inferiority one-sided, with values less than 0.05 deemed statistically significant.

Statistical analyses will be conducted in SAS version 9.3 or above (SAS Institute, Cary, N.C.), R version 3.2 or above (R Foundation for Statistical Computing, Vienna, Austria, <http://www.R-project.org>) or another validated statistical software package.

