### **17.2 Primary Endpoint**

The primary endpoint is change in gait speed (self-selected and fast) demonstrated during the 10MWT after 12 weeks of training, compared to baseline. Two hypotheses are associated with this endpoint; first, that the mean change in the Ekso intervention group will be statistically superior to that in the passive control group, as follows:

$$\begin{aligned} H_0: \mu_E &\leq \mu_P \\ H_A: \mu_E &> \mu_P, \end{aligned}$$

where  $\mu_E$  and  $\mu_P$  are the mean change in the Ekso and passive control groups, respectively. The hypothesis will be tested using a two-sample Student's t or Wilcoxon rank-sum depending upon normality of the trial data.

The second hypothesis is that the mean change in the Ekso intervention group will be statistically non-inferior to that in the active control group, as follows:

$$\begin{aligned} H_0: \mu_E &\leq \mu_A - \Delta \\ H_A: \mu_E &> \mu_A - \Delta, \end{aligned}$$

where  $\mu_E$  and  $\mu_A$  are the mean change in the Ekso and active control groups, respectively, and  $\Delta$  is the non-inferiority margin.  $\Delta$  is selected based upon the principles that it should be substantially less than the expected effect size comparing Ekso to passive control, and that it should represent a clinically acceptable margin of effect when differentiating Ekso from active control.

For this purpose,  $\Delta$  is therefore defined to be 0.055 m/s, which is one-half of the hypothesized treatment effect of Ekso over passive control as stated below, and one-eighth of the threshold of 0.44 m/s (1.0 mph) commonly used to represent gait speed associated with community ambulation.

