### **1.7 Lost to Follow-up**

Data on subjects who are lost to follow-up or who withdraw from the study will be maintained and analyzed up to the point at which they discontinued. The reason for withdrawal will be recorded if known. Subjects who discontinue participation, for whatever reason, will remain in the study and be subject to follow-up in the same manner as those who complete the study except as noted above. The only confirmed lost to follow-up subject will be the subject who dies or refuses to continue to participate in the study and thereby withdraws.

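### Both primary comparisons drop anyone without a week-12 speed although week-6 speed is measured in every arm; this can bias them if dropout follows early response

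*Protocol*

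**What the plan says.** **Missing data.** Protocol 18.1: "Values for missing data will not be imputed, but exploratory analyses may be performed using the last real assessment for that patient (LOCF".

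**Endpoint and tests.** Protocol 17.2: "The primary endpoint is change in gait speed (self-selected and fast) demonstrated during the 10MWT after 12 weeks of training, compared to baseline". For superiority over passive control: "The hypothesis will be tested using a two-sample Student's t or Wilcoxon rank-sum depending upon normality of the trial data". SAP 1.3 compares Ekso with active control through a confidence interval for the difference in means. Each comparison uses one change score per participant.

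**Analysis principle.** Protocol 17.1 says that the primary analysis "will include all available data for all enrolled subjects" and that "subjects will be evaluated according to their randomized assignment regardless of the treatment actually received".

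**Week-6 data.** The footnotes to Protocol Table 2 say "Passive Group 3 will complete all evaluations at Baseline, Week 6 and week 12, the same as Groups 1 and 2", and schedule the blinded evaluator's tests "at 6, 12, 24 weeks (midpoint, endpoint, and follow-up): up to 8 trials (total) of 10MWT", at both self-selected and fast speed.

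**Withdrawals.** SAP 1.7 says that data on subjects who are lost or withdraw "will be maintained and analyzed up to the point at which they discontinued". It also says that subjects who discontinue stay in the study and are followed like completers, apart from an exception for what was noted above, and that only death or refusal counts as confirmed loss.

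**The concern.** A participant with a week-6 speed but no week-12 speed has no value to enter in either primary test. Intent-to-treat assignment settles which arm a person is counted in; it does not supply the missing outcome. The only stated alternative is exploratory LOCF, which treats the week-6 value as if it were the week-12 value.

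The trained arms attend 36 sessions, while passive controls attend only evaluations, so loss could plausibly differ by arm and by early response. If poor early responders leave, the mean among those who remain is too high. The plan's own SDs make the Ekso arm more variable than either control, so the same dropout behaviour in every arm would not cancel. A shift towards Ekso inflates the superiority estimate. In the non-inferiority comparison it can produce a false success.

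**Working it through.** **Inputs from the documents.** Mean change (SD), Protocol 17.4 and SAP 1.8: Ekso 0.11 (0.18), active 0.078 (0.108), passive 0 (0.108) m/s. True differences are therefore 0.110 (Ekso−passive) and 0.032 (Ekso−active). The margin is 0.055 m/s (Protocol 17.2). Alpha is 0.05, two-sided for superiority and one-sided for non-inferiority (Protocol 17.1).

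**The plan's own figures reproduce.**
- Superiority, 2:1, unequal variances: passive n = (1.96 + 0.842)² × (0.18²/2 + 0.108²)/0.11² = 18.07, so 19 and 38. Welch power at 38/19 is 80.5%.
- Non-inferiority at a true difference of +0.032: Welch power is 80.2% at 37 per group.
- Enrolment: 1 − 95/127 = 25.2%. This is the most the ceiling can lose while keeping 95 evaluable.

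**Assumptions not in the documents.** Mean week-6 change is half of the week-12 mean, with the same SD. The week-6/week-12 correlation ρ is 0.5 to 0.8. The log-odds of dropout fall by 0.5 to 1.0 per 0.108 m/s of week-6 gain. All loss occurs after week 6.

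**Bias formula.** With equal SDs at the two visits, the completers mean in an arm is too high by ρ × SD × z, where z is the mean standardised week-6 change among those retained.

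**Worked case:** ρ = 0.7, slope 1.0, 25% loss in every arm. Numerical integration over the normal distribution gives z = 0.293 in Ekso and 0.213 in each control. The values differ because the same slope per m/s is steeper per SD in the more variable arm.
- Ekso: 0.7 × 0.18 × 0.293 = 0.037
- Each control: 0.7 × 0.108 × 0.213 = 0.016
- Net shift 0.021: Ekso−passive 0.131 instead of 0.110; Ekso−active 0.053 instead of 0.032

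**Ranges over ρ = 0.5, 0.7, 0.8 and slopes 0.5, 1.0:**

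| Loss Ekso/active/passive | Completers E−P (true 0.110) | Completers E−A (true 0.032) | LOCF E−P | LOCF E−A |
|---|---|---|---|---|
| 25/25/25% | 0.120–0.134 | 0.042–0.056 | 0.085–0.093 | 0.017–0.025 |
| 25/25/10% | 0.124–0.144 | 0.042–0.056 | 0.081–0.092 | 0.017–0.025 |
| 25/10/10% | 0.124–0.144 | 0.046–0.066 | 0.081–0.092 | 0.007–0.018 |
| 10/10/25% | 0.110–0.111 | 0.036–0.043 | 0.103–0.104 | 0.024–0.029 |
| 10/25/25% | 0.110–0.111 | 0.032–0.033 | 0.103–0.104 | 0.034–0.036 |

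Simulation of the same set-up agrees to within about 0.001. With a single dropout function shared by all arms and about 25% overall loss, completers give 0.119–0.131 and 0.042–0.057. With equal SDs and equal response-related dropout the bias cancels (0.110 and 0.032).

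**Size in the 25% Ekso-loss rows.** Ekso−active: (0.042 − 0.032)/0.055 = 18% to (0.066 − 0.032)/0.055 = 62% of the margin. Ekso−passive: (0.120 − 0.110)/0.110 = 9% to (0.144 − 0.110)/0.110 = 31% of the postulated effect.

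**False non-inferiority.** Simulated with the true Ekso−active difference exactly at −0.055 and 50 randomised per arm. The one-sided 5% test succeeds in 5.1% of trials when dropout is unrelated to response, and in 11% to 24% when it is related (25% Ekso loss, 10% or 25% active loss).

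**Using week 6.** Regressing week 12 on week 6 within each arm, which is valid if data are missing at random, returns 0.110 and 0.032 to within about 0.001 in every scenario.

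**Limit of that repair.** The recovery follows from letting dropout depend only on an observed week-6 value. In a simulation of the Ekso arm with half the loss before week 6, triggered by early response, the model kept about half the completers bias (for example 0.011 of 0.021, or 0.020 of 0.039). With all loss before week 6 it removed none.

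**The case against.** The strongest reply is that neither the size nor the direction of any bias is fixed by the documents, and that the simulated recovery is true by construction. Both points stand. The figures are a range under stated assumptions, some dropout patterns give almost no bias, and the model is a partial repair where loss occurs before week 6.

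Several stronger readings are tempting and should be resisted:
- A reader might infer that the primary results will be biased. The documents support only that they can be.
- A reader might take 127 against 95 as an expected 25% loss. Protocol 17.4 attributes the excess both to attrition and to departures from the postulated effects, and gives no dropout rate.
- A reader might set an Ekso−passive bias against the 0.055 margin. That margin belongs only to the comparison with active control.
- A reader might conclude that SAP 1.7 discards everyone who stops training. It largely keeps them in follow-up, and Protocol 13 (retention) and 18 (making up missed visits) also limit missing values. The two statements in SAP 1.7 need reconciling, but the intent to follow is there.

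It can also be said that SAP 1.1 mentions covariance analysis and generalized linear models. That text is generic: it discusses repeated measures for ordinal or nominal data, and its correlation-matrix item refers to dental implants. None of it is assigned to the primary endpoint. Finally, LOCF is only exploratory, so removing it does not change the primary result, and multiple imputation would serve as well as a mixed model.

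**Conclusion.** The concern holds in a limited form. The stated rules produce a completers analysis for both primary comparisons, leave week-6 speed unused, and plan no sensitivity analysis beyond optional LOCF. This does not deliver what Protocol 17.1 promises.

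If dropout is related to week-6 gain and Ekso loss is about 25%, the plan's unequal SDs lead to a shift of about 0.01 to 0.034 m/s towards Ekso in both comparisons, which matters most for non-inferiority. With 10% Ekso and 25% control loss it is near zero. LOCF is not a safe check: in the same 25% Ekso-loss scenarios it errs the other way, by an amount that depends on the assumed week-6 mean. The analysis should not depend on dropout happening to balance, and the data for a better one are already scheduled.

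**What to change.** - **Primary analysis.** Pre-specify a mixed model for repeated measures on weeks 6 and 12 in all randomised participants, with arm, visit, arm-by-visit, baseline speed and an unstructured covariance estimated separately by arm. Use its week-12 contrasts for both primary tests. Multiple imputation from the same variables is an acceptable equivalent.
- **Sensitivity analysis.** Replace LOCF with a delta-adjusted analysis that is conservative for non-inferiority, meaning it penalises missing Ekso values relative to active control. It should explicitly cover participants lost before week 6, for whom the model has no response data to use.
- **SAP 1.7.** Reconcile the two statements so that week-12 values obtained after training stops are included in the primary analysis.

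Cost: SAP wording, slightly more programming, and reliance on a missing-at-random assumption that the delta-adjusted analysis then tests. No new visits or measurements are needed.

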## **18.2 Subgroup Definitions**

Subgroup factors of interest include age, level of assistance (based on FIM-Scores), non-responders vs. responders, time since injury, spasticity, and other differences among this diverse group.

\* Exploratory analyses on these subgroups of Participants will be performed provided that there are a sufficient number of Participants in a given subgroup.

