Gait training should include outcome measures—such as speed (m/s), walking distance (m), walking index for spinal cord injury (WISCI) scores, functional independent measurement (FIM) and Ashworth scores, and visual analogue scale (VAS) pain scores. These outcomes can be used to assess those walking skills that represent requirements of everyday ambulation. Results from Lam et al's pilot study suggest the value of robotics-based (Lokomat™, Hocoma AG, Switzerland) BWSTT, which incorporates motor learning principles. Likewise, Musselman et al reported on an iSCI case series (n = 4) describing the use of a method (skill training) to retrain walking over-ground, which was intensive, variable, and relevant to daily walking. The authors concluded that retraining walking skills over-ground in challenging situations (over and around obstacles of various sizes) resulted in clinically important changes in walking speed. Median walking speed improved by 0.09 m/s for skilled walkers compared to an improvement of 0.01 m/s for BWSTT walkers.

Mehrholz et al investigated and reviewed the effect of automated electromechanical and robotic-assisted gait training devices on the improvement of walking after stroke. Twenty-three trials involving 999 participants were included. The gait-training devices in combination with physiotherapy significantly increased the odds of participants becoming independent walkers [OR: 2.39; 95% CI: 1.67, 3.43; p < 0.00001] but did not significantly increase walking velocity [mean difference = 0.04 m/s; 95% CI: -0.03, 0.11; p = 0.26] or walking capacity [6MWT = 3 m; 95% CI: -29, 35; p = 0.86]. The results should be interpreted with caution as various devices (some included electrostimulation) were studied over different durations and different frequencies, and some of the trials included participants who could walk at prior to the gait training intervention. The principal finding suggests that people in the acute phase, who are non-ambulatory at intervention onset, may benefit whereas those who are ambulatory may not benefit from this kind of training.

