### **A. Primary Objective:**

To demonstrate that a 12 week robotic gait training regimen can lead to a clinically meaningful improvement in independent gait speed on the 10 Meter Walk Test (10MWT) in community dwelling

participants with chronic iSCI.

B. Secondary Objectives:

1. To examine the economic factors such as number of physical therapists/staff required during training.
2. To analyze the physical burden on therapists assisting and supervising during training.
3. To study the influence of factors that may modify the gait recovery in the chronic incomplete SCI population (demographic, clinical, functional, psychological, balance, etc.).

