## 11. Participant and Therapist Assessments

Phone or in-person limited screening procedures are conducted to assess minimal trial inclusion. Baseline procedures establish a baseline for future comparisons. (Prior to initiating physical or psychological screening evaluations, study personnel must obtain a signed informed consent.) Participant screening can then proceed to ensure the individual meets inclusion/exclusion criteria and baseline data will be collected for comparisons. The screening and baseline procedures can occur over one or two visits.

The following information will be obtained during *screening* and, if Participant passes screening, may be used for baseline.

1. Demographic data including date of birth, gender, date and cause of injury, (self-reported)
2. Past and current medical history (self-reported)
3. List of current medications
4. Weight, height, Body Mass Index (BMI)
5. Blood pressure (sit to stand)
6. Written documentation from the participant's SCI physician verifying the participant is medically stable and cleared for full weight bearing locomotor training and does not have any conditions that would exclude the Participant including: spinal instability, unresolved DVT, decreased standing tolerance due to orthostatic hypotension, two or more spontaneous lower extremity long bone fractures in the last 48 months, hip subluxation, autonomic dysreflexia, known pregnancy (if relevant), colostomy, history of head injury or other central nervous system disorders that may impact motor planning or impulsivity, significant cardiac or pulmonary disease (screening). (see Inclusion/Exclusion criteria)
7. Current practice of standing or walking, level of assistance required, assistive devices and braces used, and any associated adverse events (self-reported)
8. Observation of a level surface wheelchair to mat transfer.
9. Range of motion for hip flexion/extension, knee flexion/extension/ ankle dorsi/plantar flexion
10. Upper extremity MMT to include: shoulder flexion/extension/abduction and elbow extension
11. Spasticity of the hip, knee and ankle muscles as assessed by the Modified Ashworth Scale at screening.
12. Skin check of back, sacrum, shins, and feet (must be done at each visit)
13. Neurological exam will be obtained using the ISNCSCI examination for motor and sensory testing and for designation of AIS and ISNCSCI motor scores of UEMS and LEMS

See Appendix A for description of assessments.

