If the participant continues to meet criteria for this study the following data will be collected as *baseline data*. **NOTE: All Participant evaluations are conducted outside of Ekso, BWSTT, or BWS for overground walking. Baseline examinations may not occur more than 30 days prior to initiation of the training regimen:**

1. 10 Meter Walk Test (10MWT), at both self-selected and fast speeds
2. GAITRite Pressure Map for Temporospatial Gait Parameters (if site has one)
3. Timed Up and Go (TUG)
4. 6 Minute Walk Test (6MWT)
5. Spinal Cord Injury Functional Ambulation Inventory (SCI-FAI)
6. Walking Index for Spinal Cord Injury (WISCI II)
7. Upper and Lower Extremity Muscle Strength
8. Berg Balance Scale
9. The Spinal Cord Assessment Tool for Spastic Reflexes (SCATS)
10. Spinal Cord Independence Measure III (SCIM-III), Mobility subscale only, by interview
11. Modified Ashworth Scale
12. Spinal Cord Injury Spasticity Evaluation Tool (SCI-SET)

13. Numeric Rating Scale for spasticity
14. International SCI Quality of Life Basic Data Set
15. Epidemiological Studies Depression Scale (CES-D 10)
16. Borg Scale for maximal Rate of Perceived Exertion (collected at baseline 6MWT and at training session 1)
17. International SCI Pain Basic Data Set
18. Modified International SCI Bowel Function Basic Data Set
19. Modified International SCI Lower Urinary Tract Basic Data Set

See Appendix A for description of assessments.

The following data will be collected *per session*:

1. Any adverse events/complications (related to Participant or staff) noted following prior training session and during present session
2. Assessment of skin integrity of the anterior and posterior torso, anterior tibia, sacral area and bilateral feet (before and after training)
3. Walk time\*
4. Stand time\*
5. Seated rest time
6. Number of steps total and in each mode\* or number of steps at each BWS%
7. Time spent in each mode\* or time spent at each BWS%
8. Any equipment used for training, including type of assistive device and braces
9. Number of therapists/staff required at each training session to ensure the safety of the Participant and to complete the training session goals
10. Amount of assistance (e.g. min, mod, max) as reported by staff members at each training position (hips, trunk, right LE, left LE, etc.)

\* For Group 1 Participants, these data are *automatically collected* by Ekso (in Ekso Pulse) at the end of each training session

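### Two of the five named exploratory subgroup factors in protocol section 18.2 cannot be used as written: responder status is fixed after randomisation, and FIM is not collected.

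*Protocol*

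**What the plan says.** Protocol section 18.2 gives the list: "Subgroup factors of interest include age, level of assistance (based on FIM-Scores), non-responders vs. responders, time since injury, spasticity, and other differences". The five named factors are therefore age, FIM-based assistance, responder status, time since injury and spasticity, and the list is left open at the end. The two at issue here are "level of assistance (based on FIM-Scores), non-responders vs. responders". The section limits their standing: "Exploratory analyses on these subgroups of Participants will be performed provided that there are a sufficient number of Participants in a given subgroup".

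The section does not define a responder. Two definitions are available elsewhere:

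- SAP section 1.4 defines an Intervention Responder by a gait-speed criterion of one-eighth of 0.44 m/s (0.055 m/s) together with freedom from an intervention-related complication.
- Protocol section 4 has a secondary endpoint counting participants who reach an MCID of 0.15 m/s on the 10MWT, without calling them responders.

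The only other mention of FIM is in the background, protocol section 1, in a list of measures that gait-training studies should include: "functional independent measurement (FIM) and Ashworth scores".

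Protocol section 2, secondary objective 3, reads "To study the influence of factors that may modify the gait recovery in the chronic incomplete SCI population" and adds demographic, clinical, functional, psychological and balance factors as examples. It does not refer to section 18.2, nor does section 18.2 refer to it.

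Neither document gives cut-points or an interaction test for the section 18.2 factors. The subgroup analysis listed in SAP section 1.1 covers GAITRite gait parameters, which are outcomes.

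**The concern.** A subgroup factor for a treatment effect should be fixed before treatment can influence it. Responder status is not. Under either available definition it is derived from the 10MWT after randomisation, which is also the test used for the primary endpoint. Arms compared within responders, or within non-responders, are no longer the groups that randomisation made comparable. The resulting difference could be read as a finding about who benefits from the device when it comes from the split itself.

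The FIM factor has a simpler problem: there will be no FIM score to group by. Several other assistance measures are recorded, and the plan does not say which one takes its place. Until one is named, the choice stays open, possibly until results are known.

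**Working it through.** **Is FIM collected?** It does not appear in the screening, baseline, per-session or every-third-session lists of protocol section 11, in Tables 2 and 3, in Appendix A or in the SAP. Assistance is recorded in these ways instead:

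- at screening, by self-report: "Current practice of standing or walking, level of assistance required, assistive devices and braces used";
- at each training session: "Amount of assistance (e.g. min, mod, max) as reported by staff members at each training position", which exists only for participants in training and only after randomisation;
- through WISCI II at baseline and at weeks 6, 12 and 24, which also reflects devices and braces;
- as the level of assistance during the 6MWT (Appendix A).

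**Are the other three factors usable?** Yes. Date of birth and date of injury are taken at screening. Spasticity is measured at screening (Modified Ashworth Scale) and at baseline (Modified Ashworth Scale, SCATS, SCI-SET).

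**Inputs for the responder split.** Protocol section 17.4 gives mean change and SD in m/s: Ekso 0.11 and 0.18; active control 0.078 and 0.108; passive control 0 and 0.108. The plan states no figure for section 18.2, so I first checked that these inputs reproduce its sample size.

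- Superiority, 2:1, two-sided 0.05, 80% power: passive n = (0.18²/2 + 0.108²)(1.960 + 0.842)²/0.11² = 18.07, rounded up to 19, with 38 on Ekso. This agrees with the plan.
- Non-inferiority, one-sided 0.05, with distance to the margin 0.055 + 0.032 = 0.087: n = (0.18² + 0.108²)(1.645 + 0.842)²/0.087² = 35.99 per group, rounded up to 36. A t-based calculation gives 79.2% power at 36 and 80.2% at 37, so the plan's 37 is reproduced.

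**Formula.** Assume changes are normal with mean μ and SD σ in each arm, and call a participant a responder if the change is at least c. I read the SAP speed criterion as a change of at least 0.055 m/s and leave its complication component out. With a = (c − μ)/σ:

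- responder share = 1 − Φ(a)
- mean in responders = μ + σφ(a)/(1 − Φ(a))
- mean in non-responders = μ − σφ(a)/Φ(a)

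**Results (m/s).**

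| Cut c | Arm | a | Responder share | Mean, responders | Mean, non-responders |
|---|---|---|---|---|---|
| 0.055 | Ekso | −0.306 | 62.0% | 0.221 | −0.070 |
| 0.055 | Active | −0.213 | 58.4% | 0.150 | −0.023 |
| 0.055 | Passive | 0.509 | 30.5% | 0.124 | −0.054 |
| 0.15 | Ekso | 0.222 | 41.2% | 0.280 | −0.009 |
| 0.15 | Active | 0.667 | 25.2% | 0.215 | 0.032 |
| 0.15 | Passive | 1.389 | 8.2% | 0.199 | −0.018 |

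| Comparison | True difference | Cut | In responders | In non-responders |
|---|---|---|---|---|
| Ekso − passive | +0.110 | 0.055 | +0.097 | −0.016 |
| Ekso − passive | +0.110 | 0.15 | +0.081 | +0.009 |
| Ekso − active | +0.032 | 0.055 | +0.070 | −0.047 |
| Ekso − active | +0.032 | 0.15 | +0.065 | −0.041 |

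No baseline modifier enters this model. The contrast between strata depends partly on Ekso's larger postulated SD. If Ekso also had SD 0.108, then at c = 0.055 its responder mean would be 0.11 + 0.108 × 0.3504/0.6947 = 0.164 and its non-responder mean 0.11 − 0.108 × 0.3504/0.3053 = −0.014. The Ekso-passive difference would then be about +0.041 in both strata, still far below 0.11. So the distortion does not depend on unequal SDs, although its pattern does.

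At the planned 19 passive controls, the expected number of passive responders is 0.305 × 19 = 5.8 at 0.055 m/s and 0.082 × 19 = 1.6 at 0.15 m/s.

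**The case against.** The strongest reply is that section 18.2 nowhere says the arms will be compared within responders or within non-responders. It promises only exploratory analyses, and a description of how responders differ from non-responders at baseline would be legitimate. That stands as a possible reading. But the text lists responder status beside age and time since injury as a subgroup factor, so it also permits the invalid comparison. The figures above show what would follow if that comparison were made; they do not show that the plan commits to it.

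A reader might infer more than the documents support:

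- **That secondary objective 3 cannot be answered.** The objective is wider than section 18.2 and depends on neither defective factor. Age, time since injury, spasticity, the Berg Balance Scale and CES-D 10 are all collected before training.
- **That responder status simply is the primary outcome.** The SAP version is a composite of speed and complications, and the protocol leaves the term undefined.
- **That the assistance factor must be chosen after the data are seen.** A collected measure can be named before analysis. The plan just has not done so.

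It is also fair to say that no single cut-off is attached to the word responder in section 18.2, so both are shown. SAP section 1.4 states its complication criterion and success rule for the Ekso and active control groups only, so applying the 0.055 m/s cut to passive control is an illustration.

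**Conclusion.** The point holds for two of the five named factors. Responder status is determined after randomisation, and a treatment comparison within its strata would misstate the effect. Against a true Ekso-passive difference of 0.11 m/s, the apparent difference ranges from −0.016 to +0.097 m/s across the two cuts and two strata. For Ekso against active control the apparent sign reverses in non-responders at both cuts. These sizes rest on normal changes, the section 17.4 means and SDs, and a responder rule based on speed alone.

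The FIM subgroup cannot be formed because the trial does not collect FIM; this needs no assumption.

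The consequence is limited. The analyses are exploratory and conditional on numbers. The primary comparisons, the sample size and the SAP success criteria do not depend on them, and secondary objective 3 remains open to analysis. This is a minor but worthwhile correction.

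**What to change.** Amend protocol section 18.2 and carry the change into the SAP:

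1. Remove responder status as a subgroup factor. State which responder definition applies, and analyse response as an outcome with baseline predictors.
2. Replace the FIM reference with one pre-training assistance measure that is already collected, named before analysis. Baseline WISCI II is one option, with a note that it also reflects devices and braces. The self-reported screening item is another. The per-session record is unsuitable because it is made after randomisation and only in those who train.
3. Assess each baseline factor by a treatment-by-factor interaction in an exploratory linear model (ANCOVA) of 10MWT change, with any cut-points stated in advance. A separate model is needed because the primary test in section 17.2 is a two-sample t or Wilcoxon test, which has no interaction term. SAP section 1.1 mentions analysis of covariance only in general terms.

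The cost is a few sentences and a small amount of extra exploratory analysis. No new data, visits or participants are needed.
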